## 5.0 Number of Subjects

**Targeted / planned enrollment.** We will enroll a total of ***N = 25*** participants, 18-65 years of age (inclusive), who meet full DSM-5 criteria for PTSD. Participants will be recruited from all racial, ethnic, and gender categories. Women and minorities will be included in the study. In FY 2014, the PCT averaged 25.3 new referrals per week (11% female, 36% Black, 4% Hispanic / Latino). The consistency of PTSD referrals will greatly facilitate recruitment for the proposed research.

**Table 2. Targeted/Planned Enrollment**

**Total Planned Enrollment: *N = 25***

---

TARGETED/PLANNED ENROLLMENT: Number of Subjects			
Ethnic Category	Sex/Gender		
	Females	Males	Total
Hispanic or Latino	0	1	1
Not Hispanic or Latino	3	21	24
Ethnic Category: Total of All Subjects*	25		
Racial Categories	Sex/Gender		
	Females	Males	Total
American Indian/Alaska Native	0	0	0
Asian	0	0	0
Native Hawaiian or Other Pacific Islander	0	0	0

Black or African American	1	8	9
White	2	14	16
Racial Categories: Total of All Subjects*	3	22	25

## 6.0 Setting

**Outcome assessment visits.** All participants will be assessed using a standard battery of clinician-administered and self-report outcome assessments at pre-treatment, post-treatment (1-week after completing treatment), and at a 1-month follow-up visit. These outcome assessments will be conducted entirely remotely via VVC or a comparable VA-approved videoconferencing platform (e.g., VVC Now, WebEx, Microsoft Teams, etc.).

**Remote telehealth treatment visits.** All treatment visits, which consist of 60 min. sessions including imaginal exposure (45 min.) followed by emotional processing (~15 min.) will take place entirely through telehealth using VVC, or if needed, a comparable VA-approved videoconferencing platform (e.g., WebEx). Note that telehealth delivery of trauma-focused therapy is already standard practice in the Charleston PCT, and our group has consistently demonstrated high-fidelity delivery in standard care, with robust clinical gains on par with carefully designed and executed RCTs, as documented in several peer-reviewed reports (e.g., Tuerk et al, 2018).

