### 3.0 Intervention to be studied.

**Study Overview.** In this open-label pilot, we will recruit 25 veterans with PTSD from the Ralph H. Johnson VAMC PTSD Clinical Team (PCT), as overseen by Col, licensed clinical psychologist, and Section Chief, [name]. Massed imaginal exposure will be delivered via VVC or any other VA approved telehealth platform, modeled after the in-person protocol of Zoellner et al., (2017). Following the initial assessment of PTSD and related symptoms and impairment, all veterans will receive six daily 60-minute telehealth sessions focusing on imaginal exposure therapy (details below). The initial assessment will

be repeated at 1-week post-treatment and 1-month post-treatment completion. As an open-label, feasibility pilot study, there is no control arm.

**Intervention: VVC-delivered Massed Imaginal Exposure.** Consistent with Zoellner et al., (2017), six, 60- minute daily sessions of imaginal exposure will be conducted based on the PE manual (Foa et al., 2007). Session 1 will include rationale for imaginal exposure and common reactions to trauma. Sessions 2-6 will focus on imaginal exposure (45 minutes) and processing (15 minutes), with later sessions focused on the most distressing aspect of the trauma memory. The final session will include relapse prevention. Between-session assignments will include listening to audio recordings of sessions at least once. All sessions will be delivered within a 10-day window. If participants do not respond, they will be offered additional services at no additional cost or loss of benefits for which they would otherwise be entitled.

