## 9.0 Study Design / Methods

### Overview.

This pilot project will implement an open-label single-arm design to address our specific aims to establish the safety, feasibility, tolerability and acceptability of massed imaginal exposure therapy for PTSD delivered via telehealth to Veterans with PTSD, and to obtain a preliminary estimate of efficacy (i.e., to support adequately powered follow-up studies employing group-randomized designs). All participants (***N = 25***) will receive a total of six-60 min. therapy sessions, delivered via VVC or a comparable VA-approved platform. Outcome assessments consisting of clinician-administered interview measures, self-report measures, and collection of remote affective and physiological indices derived from webcam footage will occur at pre-treatment, and at 1-week and 1-month following

treatment completion. Assessment instruments and procedures are detailed in the following sections.

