### Primary Outcome Measures

**Treatment Dropout/Completion.** We will collect data on treatment completion, to include the number of treatment sessions and assessment visits attended, via chart review from CPRS.

**Treatment Non-Compliance.** We will collect data on treatment compliance, including completion of in-session and between-session assignments, as determined by chart review and self-report.

**Satisfaction with Therapy and Therapist Scale - Revised (STTS-R).** The STTS-R is a 13-item Likert-type self-report scale designed to assess patient satisfaction with therapeutic services and providers (Oei & Green, 2008). This instrument will be administered at the post-treatment and 1-month follow-up time-points.

**Technology and Treatment Satisfaction Questionnaire (TTSQ).** The TTSQ is a 14-item self-report measure developed by the investigators. Items assess satisfaction, acceptance, tolerability, perceived utility and treatment outcome-related expectancies related to incorporating the remote affective physiology procedures into the assessment procedures (see below), as well as opinions about incorporating such measures into routine care. Both patients and

providers will complete slightly different versions of this measure, addressing the same items, but adapted appropriately for wording. This instrument will be administered at the post-treatment time-point.

**Clinician-Administered PTSD Scale for DSM-5 (CAPS-5).** The CAPS-5 is a structured interview for diagnosis of PTSD and is widely considered the gold-standard assessment (Blake et al., 1995; F. W. Weathers et al., 2018). The CAPS-5 will be administered at pre-treatment, post-treatment, and the 1-month follow-up visits, and will be used to evaluate inclusion criteria and as a comparative criterion to assess relations between our objective measurements and severity of trauma-related symptoms and functional impairments.

**PTSD Symptom Checklist for DSM-5 (PCL-5).** The PCL-5 is a 20-item self-report measure of PTSD symptom severity based on the DSM-5 (Wortmann et al., 2016). This measure will be administered at pre-treatment, post-treatment, and the 1-month follow-up, serving as a primary self-report outcome measure. It will also be administered at the beginning of each treatment session, to index trajectories of change over the course of treatment.

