**Columbia-Suicide Severity Rating Scale (C-SSRS).** The C-SSRS is a widely used standard assessment of lifetime and follow-up suicidality, including thoughts of intent, methods, plans, and preparatory efforts, as well as suicidal and self-harm behaviors (Posner et al., 2011). This instrument will be administered at the pre-treatment, post-treatment, and 1-month follow-up time-points.

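### Post-baseline visits are dated from treatment completion, so a Veteran who stops early has no dated outcome visit and may lack the STTS-R and any post-baseline C-SSRS

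*Combined protocol and SAP*

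**What the plan says.** Three places fix the timing of the post-baseline visits.

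- Section 3.0, Study Overview: the initial assessment will "be repeated at 1-week post-treatment and 1-month post-treatment completion".
- Section 6.0, Outcome assessment visits: "post-treatment (1-week after completing treatment), and at a 1-month follow-up visit". The same sentence applies the battery to every participant.
- Section 9.0, Overview: outcome assessments "will occur at pre-treatment, and at 1-week and 1-month following" treatment completion.

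The Figure 1 legend is looser and speaks only of time after treatment.

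Two instruments depend wholly on these visits after baseline. For the STTS-R, Section 9.0 says: "This instrument will be administered at the post-treatment and 1-month follow-up time-points". For the C-SSRS it says: "This instrument will be administered at the pre-treatment, post-treatment, and 1-month follow-up time-points". The schedule table agrees and shows neither during treatment. The TTSQ does not replace the STTS-R, because its items are "related to incorporating the remote affective physiology procedures into the assessment procedures".

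Sections 8.0 and 12.0 deal with Veterans who leave, but only as withdrawal from the study. Section 12.0 adds a meeting with the PI to explain the withdrawal and consider further care. No outcome measure is attached to it.

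**The concern.** Treatment completion is a date that an early stopper never reaches. Staff who follow the text literally have no day on which the STTS-R or C-SSRS falls due for that Veteran, and no early-termination assessment takes its place. Because stopping therapy is not separated from leaving the study, the natural course is that contact for research purposes ends.

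The loss would not be random. A Veteran who stops because the treatment is hard to accept is the one whose satisfaction rating is most informative. Section 8.0 also names imminent suicidality and intolerance of the procedures as grounds for withdrawal. Section 10.0 plans descriptive statistics for safety and acceptability, and these cannot recover a score that was never collected.

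**Working it through.** **What is and is not collected from an early stopper**

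| Information | Source | Available for an early stopper? |
|---|---|---|
| Sessions and assessments attended, compliance | 9.0, Primary Outcome Measures | Yes |
| PCL-5, PTCI-9, PHQ-9 before each session | 9.0, Treatment Process Measures | Up to the last session |
| Nightly check-in | 9.0, Treatment Procedures | While in treatment |
| Adverse events, PHQ-9 item 9 | 11.0 | Up to the last visit |
| STTS-R | 9.0 | No dated visit |
| C-SSRS after baseline | 9.0 | No dated visit |

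**The plan's own figure.** Section 4.0 enrols 25 so that 20 complete, with a 20% allowance: 20/(1 - 0.20) = 25. It reproduces.

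**Expected early stoppers, m = 25 × dropout rate**

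- 5% (Section 4.0, in-person massed treatment): 25 × 0.05 = 1.25
- 6.3% (Section 2.0, daily six-session trial): 25 × 0.063 = 1.58
- 20% (Section 4.0, allowance): 25 × 0.20 = 5. The allowance also covers missed assessments, so it may overcount stoppers.
- 28.1% (Section 2.0, Veterans): 25 × 0.281 = 7.03. This rate is cited as a reason for shortening treatment, not as a forecast for this format.

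Even at 5%, the chance of at least one stopper is 1 - 0.95^25 = 0.72.

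**Effect on the STTS-R mean.** Let m Veterans be unassessed, and suppose they would score D lower on average than those assessed. The mean of all 25 is then the observed mean minus (m/25) × D, so the observed mean is too high by (m/25) × D. The documents give no value for D; 0.5 to 2 SD is my assumption. The last two columns give the 95% half-width of a mean in SD units, t(0.975, n-1)/√n with n = 25 - m, and the D at which the shift equals it.

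| m | m/25 | D = 0.5 | D = 1 | D = 2 | Half-width | Break-even D |
|---|---|---|---|---|---|---|
| 1 | 0.04 | 0.02 | 0.04 | 0.08 | 2.069/√24 = 0.42 | 10.6 |
| 2 | 0.08 | 0.04 | 0.08 | 0.16 | 2.074/√23 = 0.43 | 5.4 |
| 5 | 0.20 | 0.10 | 0.20 | 0.40 | 2.093/√20 = 0.47 | 2.3 |
| 7 | 0.28 | 0.14 | 0.28 | 0.56 | 2.110/√18 = 0.50 | 1.8 |

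**C-SSRS.** With no event observed, the one-sided 95% upper limit is 1 - 0.05^(1/n): 11.3% at n = 25 and 13.9% at n = 20. The loss of precision is modest. Who is missing matters more.

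**Effect of re-dating.** Section 3.0 says: "All sessions will be delivered within a 10-day window". Taking session 1 as day 1, the last session attended falls between day 1 and day 10. A visit dated from it comes at most 10 - 1 = 9 days earlier than one dated from the end of the window.

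**The case against.** The strongest reply is that the plan means to assess everyone and has only worded the date loosely. Section 6.0 covers all participants, the Figure 1 legend says no more than after treatment, and dropout data are "to include the number of treatment sessions and assessment visits attended", which treats therapy and assessment attendance as separate things. Nothing bars an early stopper from the visits. This stands as evidence of intent, and it is why missing scores are an inference here. It does not supply a date. The consent pages and the figure itself are also not available, so the point is limited to the text that is.

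Second, unacceptable treatment already shows up as dropout and non-compliance, both primary outcomes, and the expected shift lies well inside sampling error. Both are right, and they limit the size of the point. They do not show why a Veteran stopped, or how the treatment was rated.

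A reader might infer that suicidality goes unmonitored in early stoppers, or that Aim 1 fails. The documents support neither. PHQ-9 item 9, adverse-event reports and nightly check-ins run up to the last contact, and endorsed suicidality leads to a full safety evaluation (Section 11.0). Aim 1 is indexed by adverse events, while the C-SSRS is listed as a secondary measure. What is missing is the structured research assessment after stopping.

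**Conclusion.** The gap holds as a matter of text: post-baseline visits are tied to completion, and early stoppers have no dated outcome visit. That the STTS-R and C-SSRS would be missing for them is likely but inferred. If so, the satisfaction component of Aim 2 and the structured post-treatment suicidality data describe mainly completers. Feasibility, tolerability judged by dropout, and the adverse-event index are affected only for the time after a Veteran stops.

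The size depends on dropout and on the assumed D. At 1 to 2 stoppers the shift is negligible beside sampling error. At 5 it approaches sampling error only if D is near 2 SD, and at 7 it can exceed it. It would be wrong to claim that the acceptability result is seriously biased at the expected dropout. The case for acting is that the scores cannot be recovered later and the change is cheap.

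**What to change.** - **Sections 3.0, 6.0 and 9.0:** for everyone who starts session 1, date both visits 1 week and 1 month after the last session attended. Recognise stopping at the latest when the 10-day window closes. If the last session was on day 1 or 2, the 1-week visit falls due on day 8 or 9, possibly before the stop is recognised; hold it as soon as it is. Completers' schedule is unchanged.
- **Content:** offer early stoppers at least the STTS-R, the C-SSRS and an adverse-event review.
- **Sections 8.0 and 12.0:** distinguish stopping study therapy from leaving the study. Leave the investigator's discretion to withdraw a Veteran, and all clinical decisions, as they are.
- **Section 10.0:** report the STTS-R and C-SSRS with the number assessed out of all who started, and with the sessions received. A Veteran who leaves after session 1 has had no imaginal exposure, so that rating does not speak to it.

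The cost is protocol and consent wording plus a few remote contacts. The compensation schedule already lists both visits for each participant ($25 + $50 = $75), so no new payment is created. Some early stoppers will decline, so the gap narrows but may not close. Veterans who enrol but never start session 1 remain outside the rule and should be counted separately.

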## 7.0 Recruitment Methods

As part of standard clinic procedures, all referrals receive a diagnostic assessment and are asked if they would like to hear about opportunities to participate in research. If Veterans respond that they are interested in being contacted about research opportunities and if they choose to begin evidence-based therapy (the modal treatment choice in the PCT), then study staff will make contact regarding potential enrollment prior to the Veteran's first therapy session. Communication between clinic and study staff will be facilitated by the PI. Research recruitment is well-integrated with the standard clinic operating procedures and similar recruitment strategies in this environment have supported successful recruitment goals of multiple studies in recent years. In support of a high likelihood of expeditious attainment of recruitment goals, in FY20, the PCT completed nearly 600 assessments for trauma-focused therapy, and triaged over 1500 consults for PTSD and related conditions via VVC. Further, the PCT has a longstanding history of supporting successful recruitment for numerous studies targeting treatment innovations.

## 8.0 Consent Process

All participants will be referred on the basis of a routine intake assessment in the PCT or another VA behavioral health clinic prior to study entry. As indicated above in the eligibility criteria, those who report clinical symptoms that suggest trauma-focused therapy for PTSD is not in their best interests will be excluded from the study and directed to alternate care as recommended by the PCT and their clinical care team. Participants who appear to meet criteria for entry into the study will be informed of the study and if they express interest, they will review

study consent, and HIPAA Authorization with study personnel (PI, study coordinator, or study evaluator).

The consent process and HIPPA authorization procedures will be completed electronically through VVC or another VA-approved videoconferencing platform, following all VA institutional guidelines pertaining to the consent and authorization procedures. Consent documents will be provided by mail, or through secure messaging, then subsequently reviewed with study personnel at the first study visit (i.e., the pre-treatment or baseline assessment). During review of consent, study staff will detail study procedures and ensure that patients understand what components are part of the study procedures and what is part of standard treatment for PTSD. Study staff will ensure that potential participants understand the study and are interested and able to complete study procedures prior to providing signed informed consent. Participants will receive in the consent document emergency contact information for use in case of acute exacerbation of symptoms. Participants will be informed that they can withdraw from the study at any time and receive alternate care outside of the study. Participants will also be informed that if they report imminent suicidality or intolerance for study procedures at any point during the protocol, they may be withdrawn from the study and receive alternate care as appropriate (i.e., inpatient hospitalization, treatment in outpatient psychiatry, etc.).

Following review of the consent documents and verbal expression of understanding and agreement by the participant, participants will be instructed to indicate their consent and authorization on the forms with their signatures. The attending study personnel will then take screen shots of the signature pages, save them on a secure, access-controlled, and encrypted VA server, and note the consent and authorization in CPRS to document study involvement.

Participants have the option to indicate they would like to be contacted for future research studies that they may qualify for on the consent documents. For participants who provide this consent, their contact information only will be stored in a separate secure data repository that will not expire upon study completion. The PI, [name] will serve as the repository administrator. The standard operating procedures for administering this repository have been outlined in the SOP associated with this protocol. Note that there will be no attempt to identify directly or indirectly any participant in their research data.

## 9.0 Study Design / Methods

### Overview.

This pilot project will implement an open-label single-arm design to address our specific aims to establish the safety, feasibility, tolerability and acceptability of massed imaginal exposure therapy for PTSD delivered via telehealth to Veterans with PTSD, and to obtain a preliminary estimate of efficacy (i.e., to support adequately powered follow-up studies employing group-randomized designs). All participants (***N = 25***) will receive a total of six-60 min. therapy sessions, delivered via VVC or a comparable VA-approved platform. Outcome assessments consisting of clinician-administered interview measures, self-report measures, and collection of remote affective and physiological indices derived from webcam footage will occur at pre-treatment, and at 1-week and 1-month following

treatment completion. Assessment instruments and procedures are detailed in the following sections.

## Assessment Procedures

### Baseline Demographic, Clinical Characteristics, and Diagnostic Measures

This study will implement a standard battery of clinician-administered and self-report measures to capture important baseline differences and changes over the course of treatment. These measures are detailed in the following sections, and the assessment schedule is provided in **Table 1** below.

Measure	Pre-tx	Tx	Post-tx	1-mo. follow-up
Trauma Interview	X		X	X
CAPS-5	X		X	X
MINI	X			
C-SSRS	X		X	X
CGI	X		X	X
DMSC	X			
LEC-5	X			
PCL-5	X	X	X	X
PTCI-9	X	X	X	X
PHQ-9	X	X	X	X
PSBQ	X		X	X
MASQ	X		X	X
SDS	X		X	X
ERNS	X			
STTS-R			X	X
TTSQ				X
SUDS		X		
PETQ			X	

**Note.** Trauma interview = remote affective and physiological measures based on video of a standardized trauma interview; CAPS-5 = Clinician Administered PTSD Scale for DSM-5; MINI = MINI Neuropsychiatric Interview Schedule; C-SSRS = Columbia-Suicide Severity Rating Scale; CGI = Clinical Global Impressions; DMSC = Demographics and Military Service characteristics Form; LEC-5 = Life Events Checklist for DSM-5; PCL-5 = PTSD Symptom Checklist for DSM-5; PTCI-9 = Posttraumatic Cognitions Inventory, 9-Item Version; PHQ-9 = Patient Health Questionnaire; PSBQ = PTSD Safety Behaviors Questionnaire; MASQ = Mood and Anxiety Symptom Questionnaire; SDS = Sheehan Disability Scale; ERNS = Emotional Reactivity and Numbing Scale; STTS-R = Satisfaction with Therapy and Therapist Scale; TTSQ = Technology and Treatment Satisfaction Questionnaire; SUDS = Subject Units of Distress Scale. PETQ = Prolonged Exposure Therapist Questionnaire.

**Demographics and Military Service Characteristics Form (DMSC).** The DMSC collects information regarding standard demographics (race, gender, age) and military service information (e.g., rank), and will be administered at the pre-treatment assessment visit.

**Life Events Checklist for DSM-5 (LEC-5).** The LEC-5 is a 17-item self-report measure that assesses prior extent of exposure to traumatic events, as defined by DSM-5 criteria (Blake et al., 1995; F. W. Weathers et al., 2018). This measure will be administered at the pre-treatment assessment to capture baseline differences in lifetime history of trauma exposure.

**MINI Neuropsychiatric Interview Schedule (MINI, version 7.0.2).** The MINI is a widely-used brief structured interview that assesses common mental health diagnoses based on DSM-5 criteria (Pinninti, Madison, Musser, & Rissmiller, 2003). This instrument will be administered at the pre-treatment assessment visit to capture common diagnostic comorbidities.

